#### 5.2.1.2 Patient demographics and other baseline characteristics

Data to be collected on patient characteristics at screening include:

-Demography (including: date of birth, age, patient initials, gender, childbearing potential, race and ethnicity, or as allowed by local regulations)

-Relevant medical history

-lung adenocarcinoma diagnosis and extent of disease, including:

Date of diagnosis

Site of active disease

Prior antineoplastic therapies (medications, radiation, surgeries)

Prior and Concomitant Medications, surgical and medical procedures

All other medications taken within 30 days before the first dose of ceritinib treatment is administered will be noted in the clinical trial medication record and updated on a continual basis if there is new change to the medication.

#### 5.2.1.3 Information to be collected on screening failures

A patient who signs an informed consent but fails to satisfy all eligibility criteria for any reason will be considered a screen failure. The reason for not entering the treatment protocol will be recorded. The demographic information, informed consent, and Inclusion/Exclusion pages will be completed for Screen Failure patients. No other data will be entered into the clinical database for patients

who are screen failures, unless the patient experienced a Serious Adverse Event during the Screening Phase (see [Section 7](#) for SAE reporting details).

Subjects who signed ICF but are considered ineligible after signing the study consent will be considered as screening failures, and data will be handled in the same manner.

The following information will be recorded for screening failure patients:

- Screening Phase Disposition page (including reason for not satisfying eligibility criteria and being started on treatment).
- Informed consent.
- Demography.
- Adverse Events (only if an SAE occurs).
- Inclusion/Exclusion Criteria.

### **5.2.2 Treatment period**

Following completion of screening procedures and verifying patient eligibility, the patient will be approved for treatment per protocol.

The study treatment phase begins on Cycle 1, Day 1 with the first administration of ceritinib and will continue to receive ceritinib treatment until disease progression by RECIST1.1 not amenable to SABR necessitating a change in systemic therapy, unacceptable toxicity, withdrawal of consent, or discontinuation of the trial for any other reason whichever occurs first. Patients who have RECIST-defined PD as assessed by the investigator but who, in the opinion of the investigator, have evidence of continued clinical benefit from ceritinib may continue to receive the study medication upon approval by the principal investigator. In such cases, these patients must continue to be followed for safety and efficacy assessments as per the schedule of assessments. Patients will be assessed as per visit schedule in Table 5-1.

There is a visit windows of  $\pm 3$  days for scheduled study assessments.

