#### Subsequent areas of progression:

As long as the study participant is on ceritinib as the sole systemic therapy, further stereotactic radiation may be delivered to up to 6 sites or organs at a time. When ceritinib is no longer the systemic agent or when new progressive sites cannot feasibly be treated with stereotactic radiation (e.g., malignant pleural effusion or site previously irradiated), study participation will end. The primary endpoint of progression-free survival will be calculated from the start of treatment to the first episode of progression.

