### **1.4 Study rationale and purpose**

Patients with *ALK*+ non small cell lung cancer will receive the current optimal therapy with ceritinib. After 10 weeks of targeted therapy, there will likely be some persisting lesions that would not have completely regressed. These persisting lesions would likely consist of cells that are less sensitive to targeted therapy. From the data summarized above [13], these persisting lesions are most to subsequently develop resistance and demonstrate progression.

To delay the onset of clinical progression, lesions that persist after 10 weeks of ceritinib therapy and are amenable to stereotactic ablative radiation will be radiated. Ceritinib will be held for 3 days before the first dose of radiation and resumed 3 days after the last dose. There is no specific window for radiation. SABR should be initiated as feasible following at least 10 weeks of ceritinib treatment.

After radiation, all patients will continue ceritinib therapy. If subsequently there is any evidence of progression, there will be an assessment of whether a repeat course of radiation is feasible. If it is feasible to repeat SABR to sites of progression, this will be performed and ceritinib resumed. If SABR is not possible, then a change in systemic therapy will be required.

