## 2.0 Study Objectives

The hypothesis is that delivering SABR to patients with persisting tumors 10 weeks after ceritinib will result in superior overall tumor control, prolong PFS for patients and lengthen the duration of ceritinib activity in patients with *ALK*+ lung adenocarcinoma.

Published experience suggests that median PFS for patients who have previously been treated with crizotinib is less with ceritinib than those who have never been treated with crizotinib (7 months vs 10 months) (Shaw et al, NEJM 2014). As a result patients enrolled on this study will be divided into cohorts on the basis of prior exposure to crizotinib.

The primary endpoint of this study will be Progression-Free Survival (PFS); defined as time from initiation of ceritinib to evidence of disease progression by RECIST 1.1, unacceptable toxicity, withdrawal of consent, or discontinuation of the trial for any other reason.

There may be progression in a specific localized region that is amenable to stereotactic radiation. If all existing lesions that enlarge and any new lesions that develop can still be effectively treated with stereotactic radiation, patients will be evaluated for repeat SABR therapy and ceritinib resumed. This will be at the recommendation of the treating physician according to standard practice. This will be defined as Time to 2nd SABR therapy and will be one of the secondary endpoints.

Similarly, if 3rd round of SABR can be safely provided with subsequent resumption of ceritinib, it will be defined as the Time to 3rd SABR therapy.

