#### 6.1.2 Disease Parameters

Measurable disease. Measurable lesions are defined as those that can be accurately measured in at least one dimension (longest diameter to be recorded) as  $\geq 20$  mm with conventional techniques (CT, MRI, x-ray) or as  $\geq 10$  mm with spiral CT scan. All tumor measurements must be recorded in millimeters (or decimal fractions of centimeters).

Note: Previously irradiated lesions are non-measurable except in cases of documented progression of the lesion since the completion of radiation therapy.

Non-measurable disease. All other lesions (or sites of disease), including small lesions (longest diameter  $< 20$  mm with conventional techniques or  $< 10$  mm using spiral CT scan), are considered non-measurable disease. Bone lesions, leptomeningeal disease, ascites, pleural/pericardial effusions, lymphangitis cutis/pulmonis, inflammatory breast disease, abdominal masses (not followed by CT or MRI), and cystic lesions are all non-measurable.

Target lesions. All measurable lesions up to a maximum of 3 lesions per organ and 6 lesions in total, representative of all involved organs, should be identified as **target lesions** and recorded and measured at baseline. Target

lesions should be selected on the basis of their size (lesions with the longest diameter) and their suitability for accurate repeated measurements (either by imaging techniques or clinically). A sum of the longest diameter (LD) for all target lesions will be calculated and reported as the baseline sum LD. The baseline sum LD will be used as reference by which to characterize the objective tumor response.

Non-target lesions. All other lesions (or sites of disease) including any measurable lesions over and above the 6 target lesions should be identified as **non-target lesions** and should also be recorded at baseline. Measurements of these lesions are not required, but the presence or absence of each should be noted throughout follow-up.

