**Study Design:**

**Purpose:** of this prospective, single-center, two cohort, non-randomized trial is to evaluate the impact of the combination of ceritinib and stereotactic radiation delivered to patients with *ALK*-rearranged adenocarcinoma. The enhanced efficacy of this combination is to be evaluated specifically with regards to prolongation of clinical benefit of ceritinib. We will also evaluate the safety of this combination of targeted therapy and radiation.

For *ALK*-rearranged patients started on ceritinib and treated with SABR to persisting lesions:  
 -PFS compared to published historical results with ceritinib alone PFS=7 month for prior crizotinib treated and 10 month for no previous crizotinib therapy (Shaw et al, NEJM 2014).  
 PFS will be defined as Time to Subsequent Systemic Therapy.

As secondary objectives, we will also report overall survival and time to 2nd and 3rd SABR for each cohort.

	Objective	Endpoint
Primary:	Cohort A: Superiority of ceritinib + SABR median PFS compared to historical control of 10 months (expected to be 20 months)  Cohort B: Superiority of ceritinib + SABR median PFS compared to historical control of 7 months	Cohort A Median PFS defined as time from initiation of ceritinib until disease progression by RECIST 1.1, unacceptable toxicity, withdrawal of consent, or discontinuation of the trial for any other reason including death.  Cohort B: Median PFS defined as time from initiation of ceritinib until disease progression by RECIST 1.1, unacceptable toxicity, withdrawal of consent, or discontinuation of the trial for any other reason including death.
Secondary:	Report Overall survival  Report Time to 2 nd SABR  Report Time to 3 rd SABR  Report proportion of patients CR/PR/stable disease at 6 and 12 months	Overall survival  Time from start of systemic therapy to first day of second course of SABR  Time from start of therapy to first day of third course of SABR  Number of patients with CR/PR/stable disease for 6 and 12 months after initiation
Safety:	Demonstrate safety of ceritinib followed by SABR	Describe toxicity and adverse events (CTCAE v.4) compared to historical controls.

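### The rule for leaving treatment differs between Sections 1.3.3/1.4 and 5.2.2; for a narrow group (growth short of RECIST progression at a non-CNS site that cannot be re-irradiated) this can move the primary PFS date

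*Combined protocol and SAP*

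**What the plan says.** **Leaving the trial.** Section 1.3.3, under subsequent areas of progression, says that "when new progressive sites cannot feasibly be treated with stereotactic radiation (e.g., malignant pleural effusion or site previously irradiated), study participation will end". It also ends participation once ceritinib is no longer the systemic agent. Under CNS metastases, the same section says that CNS progression does not end participation.

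Section 1.4 starts lower: "If subsequently there is any evidence of progression, there will be an assessment of whether a repeat course of radiation is feasible". It continues: "If SABR is not possible, then a change in systemic therapy will be required".

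**Stopping ceritinib.** Under Section 5.2.2 the patient "will continue to receive ceritinib treatment until disease progression by RECIST1.1 not amenable to SABR necessitating a change in systemic therapy". That section also allows a patient with RECIST progression who still benefits to stay on drug with the principal investigator's approval, and does not require that the lesion can be irradiated. Section 4.1.2 has a similar rule (not amenable to SABR, systemic change needed) but omits RECIST.

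**The endpoint.** Section 2.0 counts RECIST 1.1 progression as a PFS event, and also "unacceptable toxicity, withdrawal of consent, or discontinuation of the trial for any other reason". The endpoint table in Section 9.1 has "unacceptable toxicity, withdrawal of consent, or discontinuation of the trial for any other reason including death". Sections 1.3.3 and 6.1.6 date PFS at first progression, even if ceritinib is resumed. Other text conflicts with this. Section 9.1 and the Cohort B endpoint in Section 2.0 equate PFS with time to subsequent systemic therapy. Section 2.0 also lists patients whose new or enlarging lesions can be treated with SABR as not having progressed.

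**The concern.** Two physicians looking at the same scan could both follow the protocol and produce different PFS dates. Take modest regrowth at an irradiated site that cannot be treated again and does not meet RECIST progression. Under 1.3.3 and 1.4 the patient goes off trial, which is a PFS event that day. Under 5.2.2 the patient stays on ceritinib, and the event comes at a later scan.

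Each cohort is small (18 and 15) and is compared with a fixed historical median (10 and 7 months), with no concurrent control to share the ambiguity. Body scans are 8 weeks apart, so a shift of one scan is large relative to those medians for each patient affected.

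**Working it through.** **Step 1. Where the rules give different PFS dates** (PFS as worded in the main definition in 2.0 and the table in 9.1)

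| Situation | 1.3.3 / 1.4 | 5.2.2 | PFS date |
|---|---|---|---|
| New lesion or new effusion | Off if it cannot be irradiated | Off if systemic change needed; may stay with approval | Same: already RECIST progression (6.1.4) |
| RECIST progression at an existing site | As above | As above | Same: only time on drug differs |
| CNS progression | Stays (1.3.3) | May stay | Not moved by the off-trial rule |
| Growth short of RECIST progression, can be re-irradiated | Repeat SABR, stays | Stays | Same |
| Growth short of RECIST progression, existing non-CNS site, cannot be re-irradiated | Off trial: event now | Stays: event at a later scan | **Differs** |

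Only the last row matters, and the plan makes it possible. After week 10 all gross tumor should be irradiated (1.3.3), so later regrowth at a known site will often be at an irradiated one, which is an example 1.3.3 names. Section 6.1.2 says "Previously irradiated lesions are non-measurable except in cases of documented progression of the lesion since the completion of radiation therapy". It also lists "Bone lesions, leptomeningeal disease, ascites, pleural/pericardial effusions" among non-measurable disease, which covers the other example in 1.3.3 if the effusion is already present. Existing non-target disease is progression only when unequivocal (6.1.4.2), accepted in exceptional circumstances (6.1.4.3).

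**Step 2. Reproduce the plan's sample sizes.** Inputs from 9.2: medians 10 v 20 (A) and 7 v 14 (B), two-sided alpha 0.1, power 80%, accrual 36 months, follow-up 12 months. With exponential PFS and λ = ln 2 / median, the event probability is

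p = 1 − [exp(−12λ) − exp(−48λ)] / (36λ)

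and N = [(1.645/√p0 + 0.842/√p1) / ln 2]².

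- A: p0 = 0.840, p1 = 0.623, N = 17.0 (plan 18; power at 18 is 81.7%).
- B: p0 = 0.917, p1 = 0.742, N = 15.1 (plan 15; power at 15 is 79.8%).

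The stated sizes are not in dispute.

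**Step 3. Size of one scan interval.** 8 weeks / 4.348 weeks per month = 1.84 months. That is 1.84/10 = 18% of the Cohort A control median and 1.84/7 = 26% of Cohort B's, per affected patient.

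**Step 4. Effect on power when exits count as events.** The share affected (f) and the lead before RECIST progression (L) are assumptions. Section 9.3 names no PFS test, so I assumed a one-sample log-rank test against the exponential null at one-sided 0.05, the favorable half of the stated alpha. A share f of patients with PFS beyond week 10 leaves L weeks early, but never before week 10. Results are by simulation.

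| f, L | Power A | Power B |
|---|---|---|
| none | 78% | 76% |
| 10%, 8 weeks | 77% | 75% |
| 30%, 8 weeks | 75% | 72% |
| 30%, 16 weeks | 72% | 69% |

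The loss is 1 to 6 points in A and 1 to 7 in B. From the 10%/8-week to the 30%/16-week setting, the observed median falls from 20 to 19.8–18.9 months (A) and from 14 to 13.8–13.0 (B).

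A second model, using a test on the log hazard and a shift of one or two scans, agrees. At a 25% share, power goes from 82% to 77–79% (A) and from 78–79% to 72–76% (B).

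**Step 5. False-positive rate when exits count as events.** With the true median equal to the control, the rate falls: from 3.7% to 3.3–2.1% (A) and from 3.5% to 3.2–1.9% (B) over the same settings. The error is conservative.

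**The case against.** The strongest reply is that the gap closes on a sensible reading. Section 6.1 evaluates progression throughout the study by RECIST, so the progression mentioned in 1.3.3 and 1.4, both background sections, should mean RECIST progression. The stopping sentence in 5.2.2 also ends with discontinuation for any other reason, whichever comes first, so an exit under 1.3.3 is not strictly forbidden. Section 2.0 plans repeat SABR for enlarging lesions, and an irradiated lesion becomes measurable again once its regrowth is documented (6.1.2).

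Much of this stands, and it confines the problem to the last row of the table in Step 1. It does not remove it. Section 1.4 acts on any evidence of progression, and 1.3.3 names a previously irradiated site with no threshold, so a physician could reasonably read either as lower than RECIST.

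Three stronger readings are tempting but not supported:

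- *Any progression that cannot be irradiated takes the patient off trial.* Section 1.3.3 speaks of new progressive sites and exempts the CNS. Section 1.4 requires a systemic change; exit follows only through 1.3.3.
- *The false-positive rate is inflated.* If these exits were censored, simulation with the true median at the control gives 6.5–20% (A) and 5.7–16% (B). But 2.0 and 9.1 count discontinuation as an event. Section 9.10.1 names censoring in its heading and gives no rule, which is a gap but not a plan to censor.
- *Up to 64% of patients could be affected.* The figure in 1.1.4 is progression at known sites in a series not treated under this protocol. It does not measure growth short of RECIST progression that cannot be irradiated.

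**Conclusion.** The inconsistency is real and touches the primary endpoint, but its reach is narrow. The PFS date changes only for growth short of RECIST progression at an existing non-CNS site that cannot be re-irradiated. For a patient already at RECIST progression, continuing ceritinib under 5.2.2 does not move PFS as worded in the main definition in 2.0, 1.3.3 and 6.1.6.

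The likely consequence is a modest, conservative loss of power, about 1 to 7 points. That rests on an assumed 10–30% share, an assumed lead of 8 to 16 weeks, exponential PFS and an assumed test. The true share could be near zero, and then so is the effect.

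The competing PFS definitions are the larger ambiguity. If PFS were time to subsequent systemic therapy, the difference between 1.4 (change required) and 5.2.2 (change only if needed, treatment beyond progression allowed) could set the endpoint date even for patients at RECIST progression. The point lies between a minor wording matter and a change that should be made; the low cost favors making it.

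**What to change.** 1. **One off-treatment rule.** Bring 1.3.3, 1.4 and 4.1.2 into line with 5.2.2.
   - 1.3.3: *Study treatment ends when RECIST 1.1 progression cannot feasibly be irradiated and a systemic change is needed (see 5.2.2).* Keep the CNS exemption.
   - 1.4: *If such progression cannot be treated with SABR and the treating physician judges a systemic change necessary, ceritinib stops. Growth short of RECIST 1.1 progression is followed on the imaging schedule.*
   - 4.1.2, first bullet: specify RECIST 1.1. Leave the investigator-discretion bullet as it is.
2. **One PFS date.** State in 2.0, 6.1.6 and 9.1 that primary PFS is dated at first RECIST 1.1 progression or death, whether or not ceritinib continues.
3. **Exits without RECIST progression.** Step 1 alone is not enough, because discretionary exits (4.1.2, 5.2.3.2) would remain. State in 2.0, 9.1 and 9.10.1 whether such an exit is an event or censored, and add a sensitivity analysis the other way.
4. **Remove conflicting wording.** Delete time to subsequent systemic therapy as a definition of PFS (2.0 Cohort B, 9.1) and the statement in 2.0 that patients with SABR-treatable new or enlarging lesions are listed as not having progressed.

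The cost is a few sentences and one added sensitivity analysis. Sample size, visits, imaging and response criteria are unchanged, and investigators can still stop ceritinib on clinical grounds.

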### **5.2.3 End of treatment visit including study completion and premature withdrawal**

#### **5.2.3.1 End of Phase Disposition**

Patients will be evaluated upon discontinuation of the ceritinib by a clinic visit. At that time all assessments listed for End Of Treatment will be performed. A note will be entered into the clinical trial record will be completed, giving the date and reason for stopping the ceritinib treatment.

At a minimum, all patients who discontinue ceritinib treatment, including those who refuse to return for a final visit, will be contacted for safety evaluations during the 30 days following the last dose of treatment.

#### **5.2.3.2 Criteria for patient withdrawal**

Patients may voluntarily withdraw from the study (no further study data to be collected) at any time.

Patient death will be considered as a withdrawal from the study. Patients may also be withdrawn (the physician may decide to remove the patient from any further study activity) if any of the following occur:

- Adverse event(s) (see [Section 7.1](#))
- Disease progression
- Major protocol deviation
- Technical problems
- Physician decision

- Non-compliance with study treatment.
- Death
- Completed

Patients must be withdrawn if any of the following occur:

- Lost to follow-up
- Subject/guardian decision
- Pregnancy (Pregnancy will be followed for outcome)

Patients lost to follow up should be recorded as such in the clinical trial record. For patients who are lost to follow-up, the investigator will record the attempts at “due diligence” by documenting in the source documents steps taken to contact the patient, e.g. dates of telephone calls, registered letters, etc.

### **5.2.3.3 Replacement policy**

If an eligible patient is unable to start therapy with ceritinib, they may be replaced with another eligible patient if they have not received any study drug.

Apart from the above, patients will not be replaced on this study.

### **5.3.2 Safety and tolerability assessments**

Safety will be monitored by the assessments described below as well as the collection of AEs at every visit. For details on AE collection and reporting, refer to Section 7. Significant findings that were present prior to the signing of informed consent must be included in the relevant medical history/current medical conditions in the clinical trial record. Significant new findings that begin or worsen after informed consent must be recorded in the clinical trial record.

### 5.3.2.1 Physical examination

Physical examinations will include an examination of general appearance, skin, neck (including thyroid), eyes, ears, nose, throat, lungs, heart, abdomen, back, lymph nodes, extremities, and a basic nervous system evaluation. Information about the physical examination will be present in the source documentation. For the assessment schedule refer to Table 5-1. Significant findings that were present prior to the signing of informed consent must be included in the clinical trial record. Significant new findings that begin or worsen after informed consent must be recorded in the clinical trial record.

